Patient ID, Email, Phone Number sent to Info Line via salesforce email	Coordinator	X							
Baseline Surveys	Coordinator and Participant	X							
30-days of Baseline CPAP Adherence Data uploaded to portal	Coordinator and ResMed or Philips (PC Arm Only)	X							
Self-report Oxygen Adherence Baseline	Coordinator and Participant (only participants prescribed O ₂)	X							
1st Call from Respiratory Therapist Coach; confirm participant can send and receive messages to RT Group; fill out PAP use survey and O ₂ use survey, if applicable.	RT Coach and Participant (ALL participants)		X						
1st Message from Peer Coach in portal; confirm participant can send and receive messages; fill out Journal, review and set goals. Fill out My Calendar, review.	Peer Coach (PC Arm Only)		X						
1st call from peer Coach and Module 1 completed together	Peer Coach and Participant (PC Arm Only)		X						
Module 2 Fundamentals of COPD	Participant (PC Arm Only)		X						
Module 3 Fundamentals of Sleep Apnea	Participant (PC Arm Only)			X					

Self-report Oxygen Adherence 30-days	Coordinator and Participant (only participants prescribed O ₂)				X			
6-week surveys +1 week (i.e. FOSQ, CAT, ESS, PSQI, PROMIS surveys)	Participant (PC Arm Only)			X				
Module 4 PAP in Depth I	Participant (PC Arm Only)			X				
Module 5 PAP in Depth II	Participant (PC Arm Only)				X			
Module 6 Oxygen in Depth	Participant (PC Arm Only)					X		
Module 7 Oxygen with your PAP device	Participant (PC Arm Only)						X	
Self-report Oxygen Adherence 12 weeks	Coordinator and Participant (only participants prescribed O ₂)							X
12-week (+1 week) follow-up surveys	Participant (PC Arm Only)							X
Peer Coach Calls	Peer Coach and Participant (PC Arm Only)	X	X	X	X	X	X	
RT Coach Calls	RT Coach and Participant (PC Arm Only)	X				X	X	
SAE and AE reporting	ALL study staff members	X	X	X	X	X	X	X
Exit Call from coordinator	Coordinator and Participant							X

Peer Coaches

Peer coaches will generally help with the following:

- 1) The management of a chronic illness
- 2) Health literacy
- 3) Emotional Support
- 4) Social Support
- 5) Experience-based feedback
- 6) Goal-setting

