C.O.P.D Information Line peer coaches are available to participants Monday through Friday, from 9:00am to 6:00pm ET. If a participant calls the Information Line and does not reach an associate, calls are returned within 24 hours of the last business day. The C.O.P.D. Information Line Peer Coach's availability to the proactive and reactive care arms of the study is the same. There proactive care arm however, will have additional avenues of communicating with the C.O.P.D. Information Line peer coaches (i.e. the chat feature of the study portal) and will also have scheduled calls to check-in with the peer coaches on a weekly basis.

The scheduled calls between proactive care arm participants and peer coaches will be used to discuss progress in the curriculum and weekly CPAP adherence monitoring data. Peer coaches will also reach out to a proactive care arm participant if the portal indicates that they need help, this can happen in a number of ways, such as:

- A participant may indicate in a specific module lesson that they would like to speak with a peer coach
- A participant may choose to send a message to the peer coaches using the chat function within the study portal
- The participant's adherence data may show that they improved their adherence significantly and should be congratulated
- The participant's adherence monitoring data may show that they are adhering at a level below their baseline

Individuals in the reactive care arm will be given the C.O.P.D. Information Line number and told that they can call it whenever they wish, however, they will not have scheduled calls with peer coaches and their study portal data will not trigger peer coaches to call them when they are having a particularly successful or difficult week.

Individuals in the proactive care arm will likely speak with Information Line Coaches at least once a week during their initial seven weeks in the study. Peer-coaches will also be very important in providing emotional and social support to all participants.

Additionally, there will also be certified Respiratory Therapists who are providing peer coaching from the perspective of a caregiver.

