Accessing the online curriculum, health monitoring data and peer coaching present minimal risk to study participants. Thus, the project was deemed to not need a data-safety monitoring board.

Overarching approach to analyses

Preliminary analyses will begin by examining the distribution of study variables and provide descriptive statistics (e.g., mean, median, standard deviation, quartiles for continuous variable, frequency and percentage for categorical variables) about the study population. Patient characteristics will be compared among study arms by a series of Kruskal-Wallis tests and Chi-square tests (or Fisher's exact tests as appropriate). Variables on which the groups differ initially will be explored as covariates in subsequent analyses. In case of missing data, appropriate data analytic techniques will be used, which may include deletion, imputation, inclusion of an indicator of missing values, or pattern-mixture modeling. The primary analysis will be as intent-to-treat (including all enrolled subjects) and all analyses will be performed using two- sided tests with alpha=0.05. Analyses will be conducted using SAS and R statistical software. Analysis plans to address each hypothesis are as follows:

Study Primary Aim

Our hypothesis is that CPAP adherence at the 6-week time point will be improved in the proactive care group compared to the reactive care group. Random effects model will be used to compare the mean CPAP adherence over 6 months between proactive and reactive care groups. A random intercept will be included in the model to account for the repeated measures of CPAP

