“Alright, now let’s fill out the remaining questions in the Journal. We would like you to rate your quality of life, activity level, stress, mood, sleep satisfaction, confidence leaving the home and ‘How are you breathing today?’. We ask that you rate these from one to ten, one being that you are not satisfied at all and ten means that you are completely satisfied. Ok, please fill these out. Let me know when you are done! [Pause to allow for completion.] Great! Ok, now let’s hit submit.”

“The portal is going to log all of your responses to the Journal, so you will be able to look at your progress over time! Let’s look at that now... [Navigate participant to the graphs showing their Journal history. Confirm that the participant is also viewing the Journal entry graphs.] Alright, now that you can see the results, which of these are most important to you? What do you hope to see improve over time? [goal setting]”

“Anytime we speak with you we will ask you the following four things:”

- 1) Have you had any adverse events since we last spoke?
- 2) Have you had any changes in your oxygen prescription since we last spoke? Have you had any changes in your PAP prescription since we last spoke?
- 3) Do you have any travel plans, even for just a short weekend road trip?
- 4) How are you doing today? We want to help, if we can.

“Do you have any questions about when to call a Peer Health Coach or how to get into contact with a Peer Health Coach?”

"Thank you for your time today and we encourage you to get started on your coursework at your earliest convenience."

Voicemail Script:

"Hello, this is {INSERT PEER HEALTH COACH NAME} and I'm calling from the COPD Foundation's Information Line for [first name only, of participant]. This call is regarding the O₂VERLAP study. Please feel free to contact us for more information toll-free at [contact]. We are available Monday through Friday from 9am to 9pm Eastern (except holidays)."

Adverse Event, Questions to ask on each call:

- 1) Have you had any adverse events since we last spoke?
- 2) Have you had any changes in your oxygen prescription since we last spoke? Have you had any changes in your PAP prescription since we last spoke?
- 3) Do you have any travel plans, even for just a short weekend road trip?
- 4) How are you doing today? We want to help, if we can.

Outgoing Call:

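### The only documented adverse-event question is asked on peer-coach calls, which are scheduled for the proactive arm only, so event counts by arm would partly reflect how often people were asked

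*Combined protocol and SAP*

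**What the plan says.** **Where the question is asked.** The Peer Coach Scripts in Appendix C have a block headed "Adverse Event, Questions to ask on each call". Its first item is "Have you had any adverse events since we last spoke". The initial-call script tells participants that this item comes up whenever a coach speaks with them. An AE form is named in the list of peer-coach scripts but is not reproduced.

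**Who gets the calls.** In Table 1.0 the rows for peer-coach calls and for follow-up respiratory-therapist (RT) calls are restricted to the proactive arm. The Peer Coaches section says that proactive participants "will likely speak with Information Line Coaches at least once a week during their initial seven weeks in the study". Of reactive participants it says "they will not have scheduled calls with peer coaches and their study portal data will not trigger peer coaches to call them" in a particularly successful or difficult week. They are given the Information Line number and may ring it.

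**What both arms get.** Every participant has one RT coach call at the start of the study. The RT script asks about mask leak, skin irritation, dryness, pressure sores, daytime sleepiness and snoring. It asks oxygen users about changes in ease of breathing. It has no general adverse-event question. Table 1.0 also lists a coordinator exit call with no arm restriction, and no script is shown for it.

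**Reporting and oversight.** Table 1.0 has a row "SAE and AE reporting" assigned to all study staff. Under Data Analysis and Data Monitoring, on grounds of minimal risk, "the project was deemed to not need a data-safety monitoring board".

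**The concern.** Participants who are asked about events more often will report more of them. Here the frequency of asking is set by the randomised arm, because the prompt sits inside the intervention. If events are tabulated by arm, the proactive arm can show an excess that comes only from being asked, and events in the reactive arm can go unrecorded.

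Background events are to be expected. The protocol's introduction describes raised morbidity and mortality in overlap syndrome, and its Background section describes hospital admissions for acute exacerbations. With no monitoring board, staff adverse-event reports are the only safety information that the protocol describes. At stake is whether a reader could take the adverse-event record by arm at face value.

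**Working it through.** The plan gives no adverse-event figure to reproduce. The check is therefore a comparison of contacts, followed by an illustration of size.

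**Step 1. Scheduled contacts after randomisation, by arm**

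| Contact | Proactive | Reactive | General adverse-event question documented? |
|---|---|---|---|
| Peer-coach calls (Table 1.0; Peer Coaches section) | about 6 to 7 | 0 | Yes, every call |
| First RT call (Table 1.0; Peer Coaches section) | 1 | 1 | No; mask, sleepiness, snoring and, for oxygen users, breathing items only |
| Follow-up RT calls (Table 1.0) | yes | 0 | No |
| Coordinator exit call (Table 1.0) | 1 | 1 | No script shown |

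The range of 6 to 7 comes from six marks in the peer-coach row of Table 1.0 and from the statement of at least weekly contact over seven weeks. The table's column alignment is lost in the text, so the marks alone are not a firm count. The result is about 6 to 7 documented scheduled enquiries per proactive participant against 0 per reactive participant.

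**Step 2. What unequal asking could do to a by-arm count**

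Let p be the true proportion of participants with an event, equal in both arms. Let d be the proportion of those participants whose event is recorded. Then:

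- recorded risk = p × d
- apparent risk ratio = (p × d_pro) / (p × d_rea) = d_pro / d_rea, so p cancels
- expected number recorded = n × p × d

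The protocol randomises 330 participants, half to each arm, so n = 330 / 2 = 165. Both p and d are assumptions, because the documents give neither. I fix d_pro at 0.90 and vary the rest.

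| d_rea | Apparent risk ratio | Recorded at p = 10% | Recorded at p = 20% | Recorded at p = 30% |
|---|---|---|---|---|
| 0.90 | 0.90/0.90 = 1.00 | 14.9 v 14.9 | 29.7 v 29.7 | 44.6 v 44.6 |
| 0.70 | 0.90/0.70 = 1.29 | 14.9 v 11.5 | 29.7 v 23.1 | 44.6 v 34.6 |
| 0.50 | 0.90/0.50 = 1.80 | 14.9 v 8.2 | 29.7 v 16.5 | 44.6 v 24.8 |
| 0.30 | 0.90/0.30 = 3.00 | 14.9 v 5.0 | 29.7 v 9.9 | 44.6 v 14.8 |

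For example, at p = 20% and d_rea = 0.50, the counts are 165 × 0.20 × 0.90 = 29.7 and 165 × 0.20 × 0.50 = 16.5. The first row shows that equal asking, with equal capture, removes the artefact.

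**The case against.** The strongest reply has four parts.

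- **No planned analysis is touched.** The analysis sections cover adherence, patient-centred outcomes, sleep quality and symptoms, and heterogeneity of effect. None compares adverse events by arm. This stands. A reader might infer that the trial's main result is compromised, but the primary outcome is CPAP use transmitted from the device and does not depend on these calls.
- **Risk is low.** The study alters no care plan, its named risks are discomfort with questions and loss of confidentiality, and minimal risk is the stated reason for having no monitoring board. This stands, and it keeps the point minor. The missing board is not a fault in itself.
- **Reactive participants have other routes in.** All have the early RT call, which covers several device-related harms. A satisfaction rating of seven or lower prompts coaches to make contact again, with no arm limit stated. Staff check in with participants who fall behind. The exit call and the all-staff reporting row are not limited by arm. This stands in part: a reader might infer that reactive-arm events will be missed, and the text supports only that they can be. These routes do not equalise asking, though. Satisfaction follow-up depends on a prior contact, check-ins depend on lateness, and the reporting row says who reports, not who is asked.
- **The zero rests partly on silence.** No coordinator script or AE form is printed, the appendix workflow figures are not shown, and the peer-coach script contains placeholders still to be filled. This also stands, so the claim is limited to what is documented.

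**Conclusion.** The point holds as a minor one. As written, the plan ties documented adverse-event enquiry to arm: about 6 to 7 scheduled occasions in the proactive arm and none in the reactive arm. Any by-arm tabulation would tend to make the intervention look worse for reasons unrelated to true risk. The harm is confined to safety reporting by arm.

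Its size cannot be derived from the documents. On the assumptions of equal true risk and 90% capture in the proactive arm, the apparent risk ratio would be 1.29, 1.80 or 3.00 for reactive-arm capture of 70%, 50% or 30%. A reader might take the threefold figure as the expected distortion. It is only the far end of an assumed range, and the documents do not show where in that range the trial would fall. If an unprinted form or coordinator script already asks both arms the same question on the same schedule, citing it in the protocol would resolve the point.

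**What to change.** 1. Reconcile Table 1.0 with the Study Secondary Aims section. The table marks the 6-week and 12-week survey rows as proactive-arm only, while the analysis compares both arms on those outcomes. Until this is settled, an item added to the surveys would not reach the reactive arm as the table reads.
2. Add the same short adverse-event items for both arms to the 6-week and 12-week surveys and to the coordinator exit call, each with a defined recall period.
3. State in the analysis section that any by-arm adverse-event summary uses only these equally timed enquiries. List events raised in coach calls, or volunteered at other times, separately by source.

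The peer-coach question can stay as it is, so the intervention is unchanged. The cost is about a minute of participant time, some more events to process, and one correction to the schedule table.

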Appendix D: DatStat Security and Compliance

Data Transmission and Storage

Our servers, databases, and web presences employ multiple forms of security features, while our security protocols are designed to protect both the data itself, as well as the participants involved in data collection efforts.

Data Transmission

DatStat secure servers are registered with site certificates provided by AddTrust that provide for advanced encryption over the wire. As each user moves through the survey form, his/her responses are encrypted while in-transit between the browser and DatStat's server using SSL (Secure Sockets Layer) and 40, 56, 128 or 256-bit Public Key Encryption. For those customers hosting on their own premises, we recommend using https, which requires a secure certificate.

Data Storage & At Rest Encryption

All servers used for data collection are highly fault-tolerant and equipped with redundant, hot-pluggable power supplies, redundant network interfaces, and hot-swappable RAID disk storage. All primary servers are plugged into a monitored, uninterruptible power supply (UPS). All customer web applications and servers are hosted in servers running Windows Server 2008 R2 or later.

Each customer is allocated an individual database (no comingling customer data) on our database servers to store collected data. Data is encrypted while at rest within our database infrastructure using native encryption enabled and managed within the database server.

Server Protection

Physical security

DatStat servers are stored in a locked server cabinet/rack, which are housed in a state-of-the-art, well-ventilated data center. Physical access to servers and data backup is restricted to a minimal number of IT professionals. The facility is secured by guards who monitor all access to the building and will notify DatStat personnel of any building compromise or intrusion.

Logical security

Servers are protected from remote attacks through use of dedicated hardware firewalls (WatchGuard), with auditing enabled at the recommended settings. WatchGuard LiveSecurity keeps IT staff advised of all known security alerts. Firewalls closely monitor traffic to block suspicious packets from access to all systems.

Security patches are applied to DatStat servers on a timely and ongoing basis. Logs are created by the web servers to increase accountability and are essential in investigating incidents after the fact. The following are logged: failed and successful logins, attempts to access files/ directories without authority, successful and failed attempts to access sensitive data.

Data Backup

Database backups are conducted by DatStat on a daily basis. Backups are encrypted using 256-bit AES encryption and streamed over a private network to a secure offsite location. Secure, online restoration is available at any time for all available backups from this location. Daily backups are maintained for a week, weekly backups are maintained for a month, and monthly backups are maintained for a year.

Data Access

Access to data stored on the server is available only to designated users who log in with specified usernames and passwords. Users are logged out after a period of time. A listing of the named users with a description of their access privileges is available within the applications.

Software features

DatStat provides all the necessary functionality to create fully HIPAA Compliant forms and systems. Access is tightly controlled and limited to authorized individuals using the following safeguards:

- Roles and privileges defined by data owners
- Stringent password requirements, such as minimum length, change and reuse frequency, encryption, uniqueness, and expiration.
- User names that are unique, tied to an individual, and never deleted (to prevent reuse)
- Automatic log off and lockouts, with email notification to system administrator/security staff
- Limited and controlled delete capabilities for authorized users only

DatStat products are developed and backed by a complete software engineering team, including software architects, software engineers, and support/QA engineers. Their work is guided by more than 20 standard operating procedures and supervised by our highly experienced Chief Product Officer. Biographical information for our executive team members can be found at <http://www.datstat.com/leadership> and resumes for key staff are available upon request.

DatStat provides regular updates (maintenance releases and new versions) to customers as part of their annual license fee).

Standard Operating Procedures (SOPs)

DatStat employs a variety of Standard Operating Procedures in the areas of HR, IT, Support, Consulting, and Engineering to ensure customer security and patient privacy. At all times and notwithstanding any termination or expiration of contract, DatStat will hold information in strict confidence and will not disclose PHI or other confidential information to any third party.

The following SOPs are in place at DatStat to ensure staff compliance with HIPAA regulations as well as business continuity in the event of a disaster or other emergency.

Personnel Clearance

DatStat requires all employees to pass a criminal background check and to sign the *DatStat Inc. Employment, Confidential Information, and Information Assignment Agreement*. These steps must be completed before the start of employment.

Limited DatStat staff, including your DatStat project manager and qualified technical staff, may have access to the collected data. This access is based only on your permission and is performed in accordance with DatStat SOPs by DatStat employees who have completed proper training in the protection of PHI.

Access Control

DatStat maintains Standard Operating Procedures to ensure physical and network security. The DatStat office manager and IT specialist are tasked with provisioning and de-provisioning physical and network access as employees are on-boarded and separated from the organization. Standard Operating Procedures are also used to outline the processes in place to ensure data security and data integrity as related to federal compliance.

Privacy and Compliance

DatStat employees exhibit a core competence and sensitivity to the implementation of confidentiality and security measures required to maintain the standards associated with patient and research participant data. Moreover, each full-time and part-time DatStat employee has completed the following training courses:

- *HIPAA awareness for Business Associates*, from HIPAA Training.com or *HIPAA awareness training*, from Resource Management Inc.
- *Protecting Human Research Participants*, from NIH Office of Extramural Research
- *21 CFR Part 11 training*, from Computer System Validation

Business Continuity & Incident Management

DatStat maintains Standard Operating Procedures for incident response and disaster recovery. Furthermore, all data is stored in a secure hosting facility with redundant power supplies, seismic protection, and nearly unlimited bandwidth capabilities over a cross-configured, multi-homed

network. The data center is audited annually for SSAE 16 Type II compliance, which has replaced the well-known SAS 70 requirements.

Data Breach and Incident Response

DatStat employs hardware firewalls utilizing Watchguard Live Security to monitor for and stop intrusions, viruses, and other malicious activity, this coupled with server hardening and event logging are configured together to prevent any security incidents. In the event of an incident, DatStat IT personnel are immediately notified, an investigation begins, and customers are notified per their BAAs. Investigations include a review of firewall traffic logs, server event logs, and other data points to determine the extent of the breach, if one occurred. If a breach or other incident is determined to have taken place, any affected customers are again notified per their BAA with regards to the date and time, potential data breached or lost, and other details related to the incident as well as a timeline and roadmap to restoration of service and recovery of the system.
